The frequency of treatment-emergent adverse events (TEAEs) and study drug related adverse events (AEs) was higher in the serlopitant 1 mg and 5 mg groups compared to the serlopitant 0.25 mg group, and the frequency in all three treatment groups were higher than in the placebo group. The frequency of AEs leading to study drug discontinuation was comparable in the serlopitant 5 mg and placebo group and higher than in the serlopitant 0.25 mg and 1 mg groups. There was one serious adverse event (SAE) reported in the serlopitant 1 mg group (spontaneous abortion, considered not related). There were no deaths. The most common AEs in the serlopitant groups were diarrhea (6.2%, 1 mg group), upper respiratory tract infection (4.7%, 0.25 mg group), somnolence (4.7%, 5 mg group), nasopharyngitis (4.6%, 1 mg group), headache (4.7%, 5 mg group), urinary tract infection (3.1%, 5 mg group), dry mouth (3.1%, 1 mg group), nausea (3.1%, 1 mg group), arthralgia (3.1%, 0.25 mg group), musculoskeletal pain (3.1%, 1 mg group) and pruritus (3.1%, 1 mg group). The most common AEs in the placebo group were headache (6.3%), nasopharyngitis (3.2%), upper respiratory tract infection (3.2%), urinary tract infection (3.2%) and asthma (3.2%).

TCP-102

TCP-102 was a randomized, double-blind, placebo-controlled multi-center study that evaluated serlopitant 5 mg vs. placebo for the treatment of prurigo nodularis (PN). A total of 128 adult subjects 18-80 years of age with PN were randomized to receive serlopitant or placebo in a 1:1 randomization. Subjects received a loading dose of 3 tablets on Day 1 followed by 1 tablet per day for 8 weeks. The primary efficacy endpoint was the average VAS score as recorded at the study visits. Results at Week 4 and Week 8 were the primary timepoints.

Serlopitant 5 mg was superior to placebo for the reduction of pruritus as measured by change in average VAS from baseline. For the primary endpoint, change from baseline at Week 4 and Week 8 by repeated measures analysis, the decrease from baseline was significantly greater in the serlopitant group than the placebo group, with a mean difference (serlopitant minus placebo) of -1.0 at Week 4 and -1.7 at Week 8. The mean difference at Week 2 was

also significant, -0.9. In a post-hoc analysis, 25.0% of placebo subjects and 54.4% of serlopitant subjects were 4-point responders on average VAS at Week 8.

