- Collect eDiary device, review eDiary for compliance

6.5.12 *Early Termination From the Study*

Early termination of a subject from the study may occur due to loss to follow-up, withdrawal of consent by the subject. In accordance with legal requirements and International Council on Harmonization (ICH) –GCP guidelines, every subject or his/her legal representative has the right to withdraw from the study at any time and without providing reasons. If provided, the reason (adverse event, study burden, lack of efficacy, other) a subject withdrew consent will be recorded in the electronic Case Report Form (eCRF). The PI or site staff must make every effort to contact subjects who are suspected of being lost to follow-up. Attempts to contact such subjects must be documented in the subject's source documents.

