Pregnancy in a female clinical trial subject or female partner of a male clinical trial subject is not an SAE per se. Complications of such pregnancies (for example, spontaneous abortion) may qualify as SAEs and should be reported as such even if they occur after the Follow-up visit. Any congenital anomalies/birth defects must be recorded and reported as SAEs. See Safety Form Completion Instructions for complete instructions.

7.1.6 *Worsening of Pruritus*

Pruritus should be recorded as an AE or SAE only if considered by the investigator to have worsened in severity beyond the subject's typical fluctuations.

7.2 **Methods and Timing for Recording and Reporting Adverse Events**

7.2.1 *Adverse Event Reporting Period*

Any AE occurrence during the study must be recorded on source documentation and eCRF at the site, in accordance with protocol instructions.

AEs and SAEs will be recorded from the first study drug administration through the follow-up visit. After the required follow-up visit, only SAEs that are believed to be drug-related should be reported.

After informed consent, but prior to initiation of study drug, only SAEs considered by the investigator to be caused by a protocol-mandated intervention will be collected (e.g. SAEs related to invasive procedures such as blood collection). These procedure-related SAEs should only be reported on the source documents and SAE form, not on the AE eCRF. Subjects who undergo screening procedures but are not randomized into the study will not have SAEs recorded in the clinical database.

7.2.2 *Eliciting Adverse Events*

Investigators will seek information on AEs and SAEs at each subject contact through the follow-up visit. All AEs and SAEs, whether reported by the subject or noted by authorized study personnel, will be recorded in the subject's medical record and on the AE eCRF page, and, if serious, on the SAE form. For each AE and SAE recorded, the investigator will make an assessment of seriousness, severity, and causality.

7.2.3 *Assessment of Severity*

All AEs entered into the eCRF will be graded for severity using the National Cancer Institute Common Terminology Criteria for Adverse Events (NCI CTCAE) v5.0 ("[Common Terminology Criteria for Adverse Events \(CTCAE\)](#)" 2017) to describe the maximum intensity of the adverse event.

If the AE cannot be found in the event-specific NCI CTCAE grading criteria, the investigator should use the definitions for Grade 1, 2, 3, and 4 in [Table 1](#).

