1.6 Decision Rule and Sample Size

The significance level for this study is 5% (one-sided). If the one-sided p-value is less than 5% then the null hypothesis of no treatment effect is rejected. If the one-sided p-value is additionally less than 2.5%, then the serlopitant-based regimen will have met the generally accepted level of evidence required to demonstrate efficacy.

The target sample size of 200 randomized and dosed subjects (100 per group) has been determined based upon a 1:1 allocation of subjects to treatment groups and a 5% one-sided alpha level. A sample size of 200 subjects results in at least 90% power assuming a placebo 4-point responder rate of ███% and serlopitant 4-point responder rate of ███% at Week 10.

The sample size calculations have been performed in PASS 13 (“PASS 13 Power Analysis and Sample Size Software” 2014) and used a Chi-Squared test. The primary analysis will control for the stratification factors. It is expected that this unstratified power estimate will under-estimate the true power as it does not take the variance reduction resulting from stratification into account ([Matts and Lachin 1988](#)).

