2.5.1 Primary Analysis

The difference in the primary efficacy outcome measure (WI-NRS 4-point responder rate at Week 10) between treatment groups will be summarized by treatment group. The difference in responder rates between treatment arms will be tested using a Cochran-Mantel-Haenszel (CMH) test controlling for the ‘as randomized’ stratification factors. Conceptually, the hypotheses being tested are:

$$H_0: \pi_p \geq \pi_s \qquad H_a: \pi_p < \pi_s$$

where π_p is the placebo responder rate at Week 10 and π_s is the similar measure for serlopitant.

The primary endpoint will utilize the analysis windows outlined in [Section 2.4](#), the intercurrent rules outlined in [Section 2.6](#), and the missing data rules outlined in [Section 2.7](#).

2.5.2 *Secondary Analyses*

Secondary endpoints will be summarized with descriptive statistics by time point and treatment. These summary measures will include baseline, result at the time point, and change from baseline as is appropriate for the endpoint. Missing data imputation will be limited to the WI-NRS endpoint.

The differences between treatment groups for the WI-NRS 4-point at Weeks 2, 4, 6, and 8, and 3-point responder rates at Weeks 2, 4, 6, 8, and 10 will be tested using the CMH test identical to the one used for the primary endpoint.

The change from baseline to Weeks 2, 4, 6, 8, and 10 for the WI-NRS will be tested using an analysis of variance (ANOVA) model with treatment group and stratification factor as fixed effects. A separate model/test will be performed at each time-point. [REDACTED]

CCI

[REDACTED]

The change in WI-VAS to Weeks 2, 4, 6, and 10 will be tested using a similar ANOVA model.

2.6 **Intercurrent Event**

Intercurrent events include withdrawal from the study due to lack of efficacy or rescue therapy use for treatment of worsening pruritus. Rescue therapy will be identified by the site who indicate if medications were taken to treat worsening of pruritus.

Subjects who withdraw from the study early following stopping treatment due to an intercurrent event will have WI-NRS datapoints following the events set to the larger of baseline and the last WI-NRS value prior to the event. For rescue therapy this value will be imputed from the start of rescue therapy to 4 weeks after the end of this therapy. This approach will result in subjects being defined as non-responders following the intercurrent event.

[figure not shown]

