2.7 Handling of Missing Data

Summary statistics will generally be reported based upon observed data. Should a determination of treatment period (on treatment or pre-treatment) be required for adverse events or concomitant medication but the corresponding date is missing or partial, the event/medication will be considered on treatment unless the portions of the date that are available indicate this is not possible.

If a subject fails to complete their eDiary for a week or more, the WI-NRS endpoints, including the primary endpoint, may be missing. In this case, the WI-NRS change from baseline value will be imputed. The approach uses the subject's last week with data. From that point forward their trajectory will be imputed based upon the trajectory of their treatment group.

The imputation approach first determines the average change between analysis weeks (see [Table 4](#)) for each treatment group. The change between analysis weeks is the difference between results at adjacent analysis Weeks (e.g. results at Week 10 – results at Week 8). Any missing change from baseline results will be imputed by combining the last known value and the treatment group mean weekly differences from that point forward. CCI

This imputation algorithm is only used if the intercurrent events (see [Section 2.6](#)) did not occur.

For the responder endpoints, the same imputation will be performed and the responder status determined based upon the change from baseline.

Missing data imputation will only be used for the WI-NRS endpoints.

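### A study withdrawal for worsening itch is a forced non-response if coded lack of efficacy, but if coded adverse event it is imputed along the arm's trajectory and can count as a Week 10 responder

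*SAP*

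**What the plan says.** - **Events that force non-response.** SAP 2.6: "Intercurrent events include withdrawal from the study due to lack of efficacy or rescue therapy use for treatment of worsening pruritus". After such an event the score is set to whichever is higher, baseline or the last score before the event, so the change cannot be below 0. Protocol 8.8.1 names the same two events.
- **Recording of worse itch.** Protocol 7.1.6: "Pruritus should be recorded as an AE or SAE only if considered by the investigator to have worsened in severity", with the further condition that the worsening exceeds the subject's typical fluctuations.
- **Withdrawal reasons.** Protocol 6.5.12: "the reason (adverse event, study burden, lack of efficacy, other) a subject withdrew consent will be recorded". Adverse event and lack of efficacy are alternatives. No visible text says which one applies when the adverse event is itself worsening pruritus.
- **All other missing WI-NRS weeks.** SAP 2.7 starts from the last week with data: "From that point forward their trajectory will be imputed based upon the trajectory of their treatment group". It applies whenever neither event in SAP 2.6 has occurred.
- **Sensitivity analysis.** SAP 2.8 and 3.4.2 specify multiple imputation within each arm and keep the SAP 2.6 rules.

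**The concern.** The plan treats leaving because itch is uncontrolled as treatment failure. Whether that principle reaches a given subject depends on which of two defensible reason codes the site enters. Coded lack of efficacy, the subject is a non-responder. Coded adverse event, with no rescue, the same subject is given the average later course of the arm. If there had been a good response before the flare, the subject can be counted as a success on the primary endpoint. Because the multiple imputation inherits the classification, it would not show how much the result depends on it.

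**Working it through.** **The plan's own figure.** The SAP states: "A sample size of 200 subjects results in at least 90% power". Both assumed responder rates are blacked out, so this cannot be reproduced. For orientation, at 100 per arm and one-sided 5%, 90% power needs for example 25% v 44.6%. The only responder rates in the documents come from a post-hoc analysis of TCP-102 ("25.0% of placebo subjects and 54.4% of serlopitant subjects were 4-point responders on average VAS at Week 8") and would give 99.7%. The point does not depend on the power figure.

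**Step 1: the imputation rule.** Let L be the last weekly change from baseline and M the arm's mean change from that week to Week 10. Under SAP 2.7 the imputed Week 10 change is L + M. The subject is a responder if L + M ≤ -4, that is, if L ≤ -4 - M. Under SAP 2.6 the change is at least 0, never a response.

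**Step 2: numbers.** The documents give no arm trajectory. Assumed: arm mean Week 10 change of -2, -3 or -4, with 50%, 70%, 85% and 95% of it reached by Weeks 2, 4, 6 and 8. After Week 4, for example, M = 0.30 × (-2) = -0.6.

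| Last week with data | M if arm mean is -2 / -3 / -4 | L needed for response |
|---|---|---|
| 2 | -1.00 / -1.50 / -2.00 | -3.00 / -2.50 / -2.00 |
| 4 | -0.60 / -0.90 / -1.20 | -3.40 / -3.10 / -2.80 |
| 6 | -0.30 / -0.45 / -0.60 | -3.70 / -3.55 / -3.40 |
| 8 | -0.10 / -0.15 / -0.20 | -3.90 / -3.85 / -3.80 |

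The last weekly mean must therefore already be about 2 to 4 or more points below baseline. A subject last seen exactly at baseline (L = 0) is imputed at -0.1 to -2.0, a non-responder. With no post-baseline week, response requires an arm mean of -4 or lower.

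**Step 3: can the flare be missed?** SAP Table 4 averages Days 8-14, 22-28, 36-42, 47-53 and 64-70. It uses its extended days only when there are fewer than seven results. With those seven days complete up to the last week seen, Days 15-21, 29-35, 43-46 and 54-59 enter no weekly value. Days 60-63 would be used, because a subject leaving then has no complete Week 10 range.

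**Step 4: one subject, two codes.** Week 4 change -3.5, flare on Days 33-35, then study exit without rescue.
- Coded adverse event: -3.5 - 0.6 = -4.1; -3.5 - 0.9 = -4.4; -3.5 - 1.2 = -4.7. Responder each time.
- Coded lack of efficacy: change at least 0. Non-responder.

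**Step 5: effect on the test.** Each reclassified subject moves an arm by 1 percentage point at 100 per arm. The check uses the unstratified z = (pS - pP) / √(2p̄(1 - p̄)/100) as an approximation to the planned CMH test. All counts are assumed.

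| Before | Responders removed (serlopitant, placebo) | After | One-sided p |
|---|---|---|---|
| 40 v 25 | 3, 1 | 37 v 24 | 0.0118 → 0.0229 |
| 40 v 25 | 3, 3 | 37 v 22 | 0.0118 → 0.0100 |
| 40 v 25 | 5, 2 | 35 v 23 | 0.0118 → 0.0307 |
| 36 v 25 | 1, 0 | 35 v 25 | 0.0456 → 0.0614 |
| 36 v 25 | 1, 2 | 35 v 23 | 0.0456 → 0.0307 |

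The p-value can move either way, depending on which arm the subjects come from.

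**The case against.** The route is narrow. It needs full exit from the study, no rescue, the adverse event code, a last weekly mean well below baseline and a flare that the weekly averages miss. Subjects who only stop drug enter a 5-week follow-up with the eDiary running (Protocol 3.1 and 5.6). From a stop on about Day 35 (35 + 35 = 70), Week 10 can be observed. SAP 3.4.1 sets no minimum number of diary days, so one entry on Day 47 would bring a flare into Week 8. SAP 2.8 reports Week 10 response by study completion, so responders among non-completers would be visible. Protocol 8.8.2 promises sensitivity analyses under other missing-data rules, and part of SAP 2.7 is blacked out.

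Most of this stands and limits the size. It does not close the gap: no visible rule classifies these withdrawals, and the one missing-data sensitivity analysis that the SAP specifies keeps the same rule.

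Stronger readings that a reader might infer are not supported:

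- *Sites must use the adverse event code.* Protocol 7.1.6 governs when pruritus is recorded as an AE, not the withdrawal reason. A site may record the AE and still choose lack of efficacy.
- *The error always flatters the subject, or favours serlopitant.* If the arm mean rises after the last week, a subject last seen at or above baseline is imputed worse than under SAP 2.6. Between arms, the net direction depends on which has more such withdrawals. TCP-102 had 3 serlopitant and 6 placebo discontinuations for any TEAE. Removing responders in that 1:2 ratio from 36 v 25 lowers p to 0.0307. The share due to itch is not given, so this does not establish a direction either.
- *A known few percent of subjects are affected.* The documents give no such rate. The 3.1% for pruritus in the TCP-101 1 mg group is AE incidence, not withdrawal.
- *The continuous WI-NRS analyses are equally affected.* SAP 2.3.2 applies the intercurrent rules to the responder endpoints, while SAP 2.6 speaks of WI-NRS data points generally, so this is unsettled.

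**Conclusion.** The gap is real and should be closed before unblinding. Two valid codes for the same clinical outcome lead to opposite values of the primary endpoint, and the specified multiple imputation does not test this. The false-responder case requires a last weekly change of about -2 to -4 or lower, under the assumed arm trajectories, and a flare outside the averaged days. The number of subjects is probably small and cannot be taken from the documents. A single reclassified subject changes one arm by 1 point, enough to cross 5% only in a close result. The net direction between arms is unknown. The conclusion rests on the visible text of SAP 2.6 and 2.7; blacked-out text could contain a rule that is not seen here.

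**What to change.** In SAP 2.6, define the withdrawal event as study withdrawal for lack of efficacy or for an adverse event of pruritus or worsening pruritus. Identify the latter by a list of MedDRA preferred terms fixed before unblinding and linked to the disposition page, and apply the existing non-response rule to both. Report the classification as SAP 2.6 now words it as a sensitivity analysis, so that the effect of the coding is visible. Align Protocol 8.8.1 or record the difference.

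Cost: one sentence, one programming link between the AE and disposition data, and one extra table. Responder counts may fall slightly in either arm. A lighter alternative is to state how such withdrawals are classified and add a sensitivity analysis counting them as non-responders. That shows the dependence but leaves the primary endpoint subject to the code chosen.

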2.7 Handling of Missing Data

Summary statistics will generally be reported based upon observed data. Should a determination of treatment period (on treatment or pre-treatment) be required for adverse events or concomitant medication but the corresponding date is missing or partial, the event/medication will be considered on treatment unless the portions of the date that are available indicate this is not possible.

If a subject fails to complete their eDiary for a week or more, the WI-NRS endpoints, including the primary endpoint, may be missing. In this case, the WI-NRS change from baseline value will be imputed. The approach uses the subject's last week with data. From that point forward their trajectory will be imputed based upon the trajectory of their treatment group.

The imputation approach first determines the average change between analysis weeks (see [Table 4](#)) for each treatment group. The change between analysis weeks is the difference between results at adjacent analysis Weeks (e.g. results at Week 10 – results at Week 8). Any missing change from baseline results will be imputed by combining the last known value and the treatment group mean weekly differences from that point forward. CCI

This imputation algorithm is only used if the intercurrent events (see [Section 2.6](#)) did not occur.

For the responder endpoints, the same imputation will be performed and the responder status determined based upon the change from baseline.

Missing data imputation will only be used for the WI-NRS endpoints.

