8.2 Handling of Missing Data

Should a determination of treatment period (on treatment, pre-treatment, follow-up) be required for adverse events or concomitant medication but the corresponding date is missing, or is a partial date, the event/medication will be considered on treatment unless the portions of the date that are available indicate this is not possible.

If a subject fails to complete their eDiary for a week or more, the WI-NRS endpoints, including the primary endpoint, may be missing. In this case, the WI-NRS change from baseline value will be imputed. The approach uses the subject's last week with data. From that point forward their trajectory will be imputed based upon the trajectory of their treatment group.

The imputation approach first determines the average change for each week for each treatment group. The difference in the weekly measures between weeks n-1 and n will be considered the change for Week n. Any missing changes will be imputed to produce and them combined with the prior known value to produce a change from baseline result. For

example, a placebo subject with known results at Week 4 but missing at Week 6 will have their Week 6 WI-NRS change from baseline imputed as $\Delta_4 + \Delta_{P(4-6)}$, where Δ_4 is the observed change from baseline result for the subject up to Week 4 and $\Delta_{P(4-6)}$ is the average placebo change from Week 4 to 6 (i.e. the average placebo decrease from Week 4 to 6).

For the responder endpoints, the same imputation will be performed and the responder status determined based upon the change from baseline and the subject's disposition and rescue medication status (See [Section 8.8](#)).

As a sensitivity analysis, a similar approach will be used where the imputation step uses multiple imputation methodology.

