In addition to the analysis windows, data will be summarized at Follow-Up. The Follow-Up assessment will be the last assessment available that is at least seven days after the end of treatment. Should no post treatment assessments be available, the subject will not have a follow-up assessment. The baseline of an endpoint (see [Section 3.2](#)) may not always occur at the baseline visit.

The eDiary WI-NRS assessments will be summarized at Baseline, Week 2, 4, 6, 10, and Follow-up. The seven days leading up to the time point (see [Table 4](#) range), will be used to create the summary measures unless the subject does not have at least seven results. In this case, as many observations available within the complete data range will be used and additional data from the extended range (see [Table 4](#)) will be used until seven data points are achieved, or the end of the extended range is reached. An example of this algorithm can be found in [Section 3.4.1](#)

Table 4 Daily Windows

Visit	Range (complete data)	Extended Range
Baseline ^a	Day -7 to -1 or Day -6 to -1, Day 1	Day -11 to -8 or Day -10 to -7
Week 2	Day 8 to Day 14	Day 15 to Day 18
Week 4	Day 22 to Day 28	Day 29 to Day 32
Week 6	Day 36 to Day 42	Day 43 to Day 46
Week 8	Day 47 to Day 53	Day 54 to Day 57
Week 10	Day 64 to Day 70	Day 60 to Day 63

^a If the diary was completed prior to dosing on Day 1 then the baseline range includes the day of dosing (Day 1) otherwise the baseline range does not include Day 1.

An additional ‘Follow-Up’ timepoint will also be created. This timepoint includes the last 7 post treatment observations that are at least 7 days after the end of treatment.

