2.8 Sensitivity Analyses, Subgroups and Covariates

Descriptive statistics for the WI-NRS responder rate at Week 10 will be provided for the subgroups indicated below. Forest plots of the difference and confidence interval for this difference will also be created. The subgroups include,

- Sex
- Age Group
 - (≤ 64 years, > 64 years)
 - (< 50 years, ≥ 50 years).
- Race - all race groups with less than 30 subjects will be combined with 'Other'

- Baseline WI-NRS (< 8.5, >= 8.5)
- Duration of chronic pruritus (< 1 yr, 1-5yrs,>5 yrs)

Additionally, the WI-NRS responder rates at Week 10 will be summarized for subject with and without the following post baseline events. These are post-baseline factors and may be correlated with treatment outcomes.

- Study Disposition
 - Completed study
 - Did not complete the study
- Ever require / did not require rescue therapy for treatment of worsening pruritus
- Treatment completion (completed treatment, did not complete treatment).

To investigate the impact of missing data, missing WI-NRS data will be derived using the method of Markov Chain Monte Carlo (MCMC) multiple imputation. Imputation will be conducted within each treatment group independently, so the pattern of missing observations in one treatment group cannot influence missing value estimations in another. The MCMC imputation will use the observed results at each timepoint. For each imputation process, 1000 imputations will be performed. To mimic the original missing data algorithm, the continuous values will be imputed and the responder status will be determined. The intercurrent events rules (see [Section 2.6](#)) will continue to be used. A CMH test, identical to the test used for the primary endpoint, will be used based upon the imputed responder status.

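### The WI-NRS imputation and its MCMC check draw only on the Table 4 windows, so diary scores recorded outside them cannot inform a missing Week 10 result

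*SAP*

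**What the plan says.** **Diary.** Protocol Appendix A, Table 3 has the subject record WI-NRS once a day from screening to the follow-up visit.

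**Imputation rule.** SAP 2.7 describes the start as "The approach uses the subject's last week with data". The step is then defined: "The imputation approach first determines the average change between analysis weeks", with a pointer to Table 4 and Week 8 to Week 10 as the illustration. The two are joined as follows: "Any missing change from baseline results will be imputed by combining the last known value and the treatment group mean weekly differences from that point" onward. A redacted block comes next. Responder status is read from the imputed change. The rule is switched off after rescue use or withdrawal for lack of efficacy, which SAP 2.6 handles.

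**Windows.** SAP 2.4, Table 4 has five post-baseline windows: Days 8–14 for Week 2, "Day 22 to Day 28" for Week 4, "Day 36 to Day 42" for Week 6, "Day 47 to Day 53" for Week 8, and Days 64–70 for Week 10. Each has a four-day extended range, used only to top up to seven values.

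**Sensitivity analysis.** SAP 2.8 says "The MCMC imputation will use the observed results at each timepoint". Step 1 in SAP 3.4.2 shows that these results are the Table 4 weekly values. Part of step 2 is redacted.

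**Protocol.** Section 8.2 says "The difference in the weekly measures between weeks n-1 and n will be considered the change for Week n". Its worked example steps from Week 4 to Week 6, and Section 8.8.1 lists only even-numbered weeks as weekly measures.

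**The concern.** Subjects with no Week 10 value are the ones whose primary responder status is constructed rather than observed. The itch scores recorded just before the gap are usually the best predictors of what follows. For some stopping days the plan collects those scores and then does not use them. That adds error to the imputed status, and the error need not cancel between arms if early diary-stopping is unequal.

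The planned check does not recover the scores either, because it takes its input from the same windows. A missing-at-random argument covers only what is in the imputation model. If stopping depends on itch recorded in Week 1 or Week 3, those scores need to be in it.

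**Working it through.** The plan's own figure, at least 90% power with 200 subjects, cannot be reproduced because both responder rates are redacted. This point does not depend on it.

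**1. Day count (Table 4).**
- Main windows: 5 × 7 = 35 of 70 days, so a complete diary leaves 35 unused.
- Extended ranges (Days 15–18, 29–32, 43–46, 54–57, 60–63): 5 × 4 = 20. Eligible days: 35 + 20 = 55.
- Never eligible after baseline: 70 − 55 = 15, namely Days 1–7 (7), 19–21 (3), 33–35 (3) and 58–59 (2). A pre-dose Day 1 entry may count towards baseline.

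**2. Where an interrupted diary restarts** (complete up to the stop, no intercurrent event).

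| Last diary day | Starting value | Recorded afterwards but unused |
|---|---|---|
| 7 | no post-baseline value | Days 1–7 |
| 21 | Days 8–14 | Days 15–21 |
| 35 | Days 22–28 | Days 29–35 |
| 59 | Days 47–53 | Days 54–59 |

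From Day 60 on, the extended range supplies a Week 10 value and nothing is imputed.

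**3. Diary ending by Day 7.** If the change starts at 0, the imputed Week 10 change in an arm is 0 + (sum of that arm's five mean steps: baseline to 2, 2 to 4, 4 to 6, 6 to 8, 8 to 10). Nothing in it is specific to the subject. With no other missing data the sum telescopes to the arm's mean change. In one simulated arm with other dropout it was −2.96 against an observed mean of −2.92. Every such subject is a non-responder if the sum is above −4 and a responder if it is −4 or lower.

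**4. Bias in the responder difference (serlopitant minus placebo).** For each arm let k be the proportion stopping in Week 1, p their true responder rate and q their imputed rate. Then

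bias = k_s(q_s − p_s) − k_p(q_p − p_p).

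All of these inputs are assumptions. Simulated trajectories had mean change levelling off at −2.2 to −2.5 on placebo and −3.2 to −3.7 on serlopitant, with stopping unrelated to outcome. They gave p_p = 22–28% and p_s = 36–44%. The SAP rule gives q = 0 in both arms. Starting from the Week 1 mean gives q_p = 6–13% and q_s = 24–38%. Pairing lower ends with lower and upper with upper gives, in percentage points:

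| k_s / k_p | SAP rule, start at 0 | Start from Week 1 mean |
|---|---|---|
| 6% / 2% | −0.06×36 + 0.02×22 = −1.7; −0.06×44 + 0.02×28 = −2.1 | 0.06×(24−36) − 0.02×(6−22) = −0.4; 0.06×(38−44) − 0.02×(13−28) = −0.1 |
| 3% / 3% | −0.03×36 + 0.03×22 = −0.4; −0.03×44 + 0.03×28 = −0.5 | 0.03×(−12) + 0.03×16 = +0.1; 0.03×(−6) + 0.03×15 = +0.3 |
| 2% / 6% | −0.02×36 + 0.06×22 = +0.6; −0.02×44 + 0.06×28 = +0.8 | 0.02×(−12) + 0.06×16 = +0.7; 0.02×(−6) + 0.06×15 = +0.8 |

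Direct simulation of the 6%/2% case agrees: −1.6 to −2.2 under the SAP rule, −0.6 to +0.1 from the Week 1 mean.

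**5. If one arm crosses −4.** With assumed mean changes of −4.1 on serlopitant and −2.5 on placebo, all Week 1 stoppers on serlopitant become responders and all on placebo non-responders. Balanced 3% stopping then gives +2.2 to +2.3 points under the SAP rule against +0.5 to +0.6 from the Week 1 mean. With 6%/2% it gives +3.4 to +3.5 against +0.4 to +0.5. The sign of the bias depends on which side of −4 the arm mean falls.

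**6. Imputation error.** With between-subject SD 2.2–2.5 and weekly noise SD 0.8–1.2, starting from the latest 7-day mean cut RMSE by 6–30% for Week 1 stoppers and 9–11% for Week 3 stoppers. Misclassification in the Week 3 group fell by 1–4 points. Repeat runs under similar assumptions gave RMSE reductions of 5–23% and 8–13%.

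**The case against.** **The start value may be settled in the redacted text.** This stands. Last week with data could be read to include Week 1, although the visible text defines no step from Week 1 to Week 2. The single-status result for Week 1 stoppers is therefore conditional. The restart from an older week after a Week 3 or Week 5 stop follows from the visible step definition.

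**The SAP follows the protocol.** This also stands. A reader might infer from the n−1 to n wording in Protocol 8.2 that the SAP dropped a required weekly step. The example in that section and the list in 8.8.1 use even weeks, so the protocol does not require one.

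**The windows are not the main cause of 0% imputed responders.** Correct. Putting one deterministic mean through the −4 cut-off causes most of it. Starting from Week 1 still under-counts: 6–13% against a true 22–28% on placebo, and 24–38% against 36–44% on serlopitant. The planned MCMC analysis draws values with variability. When stopping was unrelated to outcome, draws from the Table 4 Week 10 distribution recovered the true rate for Week 1 stoppers. It would be wrong to say that the MCMC analysis shares the single-status fault; it shares only the unused scores.

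**Few subjects are affected.** Probably so. Stopping drug does not stop the diary: drug stopped on Day 7 leads to follow-up until about Day 42 (7 + 35), with Weeks 2, 4 and 6 observed. One entry on Day 8 is enough for a Week 2 value. Entry requires at least 80% diary completion, and there is a Week 1 compliance call. Rescue use and lack-of-efficacy withdrawal go elsewhere.

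**Half of the diary is ignored only when it is complete**, and then Week 10 is not imputed. With scattered gaps the unused share of recorded days was 44%, 38% and 32% at 90%, 80% and 70% completion.

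**Conclusion.** The point holds as a modest, inexpensive improvement. Neither the primary imputation nor the MCMC check can use scores outside the Table 4 windows. For a diary ending in Week 3 or Week 5, and for one ending by Day 7, the unused scores include the most recent ones.

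Both arm means staying above −4, a 6%/2% excess of Week 1 stopping on serlopitant makes the bias about 2 points, against about 0.5 or less with weekly starting values. Balanced 3% stopping gives about half a point or less either way, with the sign reversed, and the 2%/6% pattern shows no gain. The effect is larger if the serlopitant mean passes −4. The documents give no stopping rate or trajectory, so all of these sizes are conditional. Observed Week 10 results are unaffected.

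A reader might infer that every Week 1 stopper is certain to receive the arm mean. The documents do not support that: the start value is not visible, and what would be received is the arm's summed mean change applied to the subject's own baseline.

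**What to change.** In SAP 2.7, for imputation only:

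1. Form 7-day means for all ten treatment weeks (Days 1–7, 8–14, …, 64–70) and compute arm-mean steps between adjacent weeks.
2. Start from the subject's latest week with data, Week 1 included. State the start value for a subject with no post-baseline diary entry at all.
3. Enter the same ten means in the MCMC model (SAP 2.8 and 3.4.2).
4. Say which imputed week supplies the Week 8 endpoint, because regular weeks put Week 8 at Days 50–56 and Table 4 does not.

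Endpoint weeks, Table 4 and the SAP 2.6 rules stay unchanged. If the ten-week scheme is not adopted, the SAP should at least state the start value and whether diary weeks outside Table 4 count as weeks with data.

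The cost is SAP wording and a little programming before unblinding, with no new data. The change does not cure the under-counting of responders by deterministic mean imputation; the MCMC result should be read for that.
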